2 INTRODUCTION AND STUDY RATIONALE

As few as half of sexually active youth used a condom the last time they had sex, and 14% did not use any form of contraception at last intercourse (Kann et al., 2018). This risky behavior can have lasting consequences. As many as one in four sexually active girls has a sexually transmitted disease (STD; Centers for Disease Control and Prevention [CDC], 2018c; Forhan et al., 2009), which can increase the risk of HIV and infertility (CDC, 2018b). Further, adolescent boys, particularly young men who have sex with men, are at heightened risk of HIV and other STDs, with recent data showing that 17% of new HIV infections occur among young boys and men under the age of 24 (CDC, 2018a).

New approaches are needed to engage youth in HIV prevention to curb the spread of HIV/STDs. Online, technology-based sexual health programs, also known as eHealth, mHealth, and digital health programs, are one promising tool that can be used (Lightfoot, 2012; Rapoff, 2013). Technology use is now ubiquitous among youth: 95% of U.S. teens have access to a smartphone and nearly half of these youth report they are online “almost constantly” (Smith & Anderson, 2018). Thus, online sexual health programs may be a particularly relevant way to offer information and teach skills to youth in a way that is readily available, familiar, non-threatening, and intuitive.

The number of online sexual health programs targeting youth has been steadily increasing for the past decade (for reviews, see Chavez et al., 2014; Swanton et al., 2015; Widman, Nesi, et al., 2018). Yet to our knowledge, there are no brief online interventions that provide evidence-based sex education and are tested and found effective for diverse samples of both boys and girls. Such a program, particularly one shown to be efficacious among such diverse samples, could be of significant interest to schools or community programs that would benefit from a general program that is appropriate for a wide audience of youth with diverse identities.

The purpose of this study is to provide an initial evaluation of one such program, called Health Education and Relationship Training for Teens (HEART for Teens). This brief online program was adapted from a program we originally developed for adolescent girls, called HEART for Girls (Widman, Golin, Noar, Massey, & Prinstein, 2016).

3 STUDY AIMS

Aim 1: Evaluate the feasibility and acceptability of the HEART for Teens program.

Aims 2: Evaluate the preliminary efficacy of the HEART for Teens program in a randomized controlled trial of youth from a rural school district in the southeastern U.S.

4 STUDY DESIGN

4.1 Randomized Controlled Trial

A two-arm randomized controlled trial. Arm 1: HEART intervention; Arm 2: attention-matched controlled program, called Growing Minds (Burnette et al., 2018). Participants will be assessed at pre-test and immediate-post test.

4.2 Study Population

All 10th and 11th grade students from a school district in the southeastern U.S. will be recruited to participation in this study (n recruited = 754).

4.2.1 *Inclusion Criteria*

1. Must be a 10th or 11th grade student
2. Must speak English
3. Provide written parental consent
4. Provide written student assent

4.2.2 *Exclusion Criteria*

1. Unable to speak fluent English
2. Unwilling or unable to provide parent consent or student assent

5 **QUALTRICS DATA COLLECTION**

All data collected will be directly entered and stored in the web-based Qualtrics research electronic data system. This Qualtrics database will be stored, maintained, and monitored by the NC State Office of Information Technology and the study personnel. The Qualtrics system is a secure, web-based application designed to support survey and data collection. NC State has a license to host the Qualtrics system. Access to the Qualtrics database will be carefully restricted to authorized research team members as needed to perform their job functions, pursuant to Federal regulations.

6 **RECRUITMENT**

Potential study participants will be recruited via in-class announcements at their high school. Students will be provided with an informed consent document to take home to their parent/guardian. Parents are asked to sign and return the form to indicate whether child is approved to participate in the study. All students in the 10th and 11th grades will be recruited.

7 **INFORMED CONSENT**

Written informed consent from parents will be collected via an IRB-approved informed consent document. Once parental consent is collected, study staff will explain the study to students and also provide them with a written assent form approved by the NC State IRB. Students will be allowed sufficient time to ask questions about the study and express understanding. Only students who have received parental consent and have signed an assent document will be allowed to participate in the study. Written consent/assent documentation will be stored in a secure physical or electronic server location according to standard operations approved by the NC State IRB.

8 **DATA COLLECTION PROCEDURES**

After parental consent and student assent are obtained, pre-test data will be collected using computerized Qualtrics surveys in a small group classroom setting. Participants will then be randomly assigned to either the HEART for Teens online program or to an attention-matched control program focused on cultivating academic growth mindsets, called Growing Minds (Burnette, Russell, Hoyt, Orvidas, & Widman, 2017). Random assignment to study condition will be conducted using random sampling and allocation procedures in SPSS version 24. Participants will be stratified based on sexual activity status (ever sexually active versus never sexually active). Approximately one week after pre-test, participants will complete the online intervention on a study-provided netbook computer as well as a computerized Qualtrics post-test survey in a small group classroom setting. Participants will use headphones to listen to program content and to control for any outside noise.

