10 MEASURES

10.1 Participant Characteristics. Demographic data will be collected on participant gender, age, race/ethnicity, sexual orientation, and receipt of free or reduced-price lunch (a proxy for socioeconomic status). Sexual activity status will be assessed with two items: one that inquired if participants had ever engaged in any sexual activity, including sexual touching, oral sex, and/or intercourse; and a second, if they answered “yes” to the first question, that inquired if participants had ever engaged in sexual intercourse. Additionally, among those who reported sexual intercourse, information was gathered about condom use at last sex.

10.2 Program Acceptability. Program acceptability will be assessed through a questionnaire that was adapted from prior acceptability surveys (Bauermeister et al., 2015; Widman et al., 2017). Specifically, six items will be included to assess six aspects of acceptability: 1) how much participants liked the program; 2) how much they learned from the program; 3) how much they felt the program kept their attention; 4) whether they would use information from the program in the future; 5) whether the program would be useful for girls their age; and 6) whether the program would be useful for boys their age. Items are rated on a four-point Likert scale ranging from 0 (*not at all*) to 3 (*a lot*).

10.2 Intentions. Intentions to discuss sexual health and to use condoms will be assessed with two items. The first asks how likely teens are to discuss sexual health issues, including pregnancy and STDs, with their partner(s) prior to sexual activity (communication intentions). The other item asks how likely teens are to use condoms the next time they have sex (condom intentions). Participants will be prompted to answer these questions whether or not they had engaged in sexual activity before. Response options range from 0 (*not at all likely*) to 4 (*very likely*).

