11 STATISTICAL ANALYSIS STRATEGY

11.1 Analysis Plan

First, descriptive statistics will be utilized to summarize sociodemographic variables and pre-test levels of each outcome variable. To establish pre-test equivalence, differences between groups will be assessed using *t*-tests for continuous variables and χ^2 -tests for categorical variables. Second, to assess the efficacy of the HEART intervention from pre-test to immediate post-test, linear regression analyses will be utilized to compute adjusted means and mean differences between intervention and control groups. For each outcome, the corresponding pre-test measure will be included as a covariate. Third, moderation analyses will be conducted to examine if intervention effects are moderated by gender or sexual orientation. Cohen’s *d* value will be calculated as an indication of effect size. Analyses will be completed using SPSS Version 24.

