15 PATIENT SAFETY AND MONITORING PLAN (PSMP)

15.1 Risks of Study Participation

The psychological risks directly posed by participating in this study are judged to be minimal and rare (<1%). One risk of participating in this study is that participants may feel uncomfortable answering sensitive questions about their attitudes or private/illegal behaviors (e.g., sexual activity). To reduce this risk, we will inform students that they do not have to answer any questions that they do not want to answer. They will be told that they can skip any items that make them uncomfortable or stop their participation at any time. Participants can also speak with members of the research team if they become upset, and/or the research team can provide students with referrals if they would like to speak with someone about any of the information they receives as part of this program.

Another risk of participating is that the data we are collecting is sensitive and must be carefully protected to ensure confidentiality. Several steps will be taken to protect participant survey data and academic records. This includes deidentifying all data by using only a participant ID number, and not the participant's name. We will also store data in password-protected files on our secure server. The spreadsheet linking participant names with ID numbers will be stored in a separate file from participant data and secured with a separate password. Only the PI, Co-Investigator, and Project Manager will have access to this spreadsheet.

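### Low-severity free improvement: the efficacy regression leaves out the sexual activity stratum used at randomisation, so its reported standard errors may be slightly too large

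*Combined protocol and SAP*

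**What the plan says.** - **Allocation (protocol section 8, Data Collection Procedures).** "Random assignment to study condition will be conducted using random sampling and allocation procedures in SPSS version 24". The next sentence reads: "Participants will be stratified based on sexual activity status (ever sexually active versus never sexually active". The section gives neither an allocation ratio nor a statement that balance within strata is forced.
- **Efficacy model (section 11.1, Analysis Plan).** A linear regression per outcome gives adjusted means and mean differences between arms. On covariates it says: "For each outcome, the corresponding pre-test measure will be included as a covariate". The only moderators named are gender and sexual orientation. The stratum does not appear.
- **Timing (section 8).** "Approximately one week after pre-test, participants will complete the online intervention", with the post-test in the same session, so the pre-test is the same measure about a week earlier.
- **Source of the stratum (section 10.1).** There are two items. The first asks whether participants "had ever engaged in any sexual activity, including sexual touching, oral sex, and/or intercourse". The second, for those who say yes, asks about intercourse. Section 8 does not say which item defines ever sexually active.
- **Blanks (section 15.1).** "They will be told that they can skip any items that make them uncomfortable". No section says how a student with a blank sexual activity answer is allocated or analysed.

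**The concern.** A factor used to stratify randomisation is normally carried into the analysis. When arms are balanced within strata, between-stratum differences cannot contribute to the difference between arms. A model that omits the stratum nevertheless leaves that variation in its residual, so its reported standard error exceeds the true variability of the estimate. Outcomes such as condom intentions, condom attitudes, self-efficacy and sexual assertiveness could plausibly differ by sexual experience, although the documents give no figure.

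What is at stake is a little precision. The pre-test covariate already carries most of any stable ever/never gap, so only the part of the stratum that predicts post-test beyond pre-test matters.

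**Working it through.** The plan states no sample size, power, SD or alpha for this analysis, so there is no figure of its own to reproduce.

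**Inputs.** From the documents: two strata, the pre-test as sole covariate, and 754 students approached (section 4.2). Assumed, because the documents give none of them: share ever active *p*; gap *d* between strata in within-stratum SD units, equal at both tests; within-stratum pre-post correlation *r*; and, where N matters, 300 analysed (300/754 = 40% of those approached).

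**Step 1: arms balanced within strata.** Let v = p(1−p)d².
- Residual variance without the stratum: (1+v) − (r+v)²/(1+v) = (1−r)(1+r+2v)/(1+v).
- Residual variance with the stratum: 1 − r².
- Partial R² of the stratum: v(1−r)/(1+r+2v).
- Excess interval width: 1/√(1−R²) − 1.

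With p=0.5 and d=0.5, v = 0.25×0.25 = 0.0625. At r=0.5 the variance ratio is 1.625/(1.5×1.0625) = 1.0196, and its square root is 1.0098, an excess of 0.98%. Excess width at p=0.5:

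| Gap d | r=0 | r=0.3 | r=0.5 | r=0.6 | r=0.8 |
|---|---|---|---|---|---|
| 0.2 | 0.49% | 0.27% | 0.16% | 0.12% | 0.05% |
| 0.3 | 1.09% | 0.59% | 0.37% | 0.27% | 0.12% |
| 0.5 | 2.90% | 1.57% | 0.98% | 0.73% | 0.33% |

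Equal strata are the least favourable share. At p=0.4, r=0.6, d=0.5: v = 0.24×0.25 = 0.06, R² = 0.024/1.72 = 1.4%, excess 0.70%.

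**Step 2: gap remaining after pre-test adjustment.** If *d* is in residual SD units, the excess is √(1+v) − 1. For d=0.5 this is 1.98% at p=0.2 and 3.08% at p=0.5. The units matter. A gap of 0.5 in within-stratum outcome SD, absent at pre-test, gives √(1 + 0.0625/0.75) − 1 = 4.1% at p=0.5, r=0.5, but that gap would have to open within the week.

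**Step 3: simulation** (1:1 within strata, d=0.5, p=0.5, 4,000 runs per setting).
- Excess width was 1.57% at r=0.3 for both N=200 and N=754. At r=0.5 it was 0.99% and 0.97%.
- At N=754, r=0.3, the true sampling SD was 0.0696 with and without the stratum. The mean reported standard error was 0.0706 without it and 0.0695 with it.
- Null rejection rates were 4.4% to 5.3% without the stratum and 4.8% to 5.3% with it.

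Omission therefore overstates the reported standard error. It hardly changes the estimate's real variability.

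**Step 4: balance not forced.** The planned model's standard error is then valid. An extra covariate costs about 1/N in variance, so it pays only when R² exceeds 1/N. At N=300, p=0.4, r=0.6: 0.4v/(1.6+2v) = 1/300 gives v = 1.6/118 = 0.0136 and d = √(0.0136/0.24) = 0.24 SD. If the stratum adds nothing, the cost in width is about 1/(2×300) = 0.17%.

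**Step 5: blanks.** Dropping a fraction m of students widens the standard error by 1/√(1−m), so the gain is cancelled when m = R². At p=0.4, r=0.6, d=0.5 that is 1.4%, or about 4 of 300 students. At m=5% the result is √(0.986/0.95) − 1 = 1.9% wider than the planned model.

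**The case against.** The best case for leaving the plan alone is that nothing of consequence changes. The trial is preliminary, its size is set by consent, and there is no power target to miss. Pre-test adjustment, the main precision gain, is already planned. Section 11.1 promises adjusted means, mean differences and Cohen's d, not intervals. If balance is not forced and the gap is below about 0.24 SD, adding the stratum gains nothing. If blanks are dropped, it can do harm.

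All of this stands as a limit on size, and it is why the fix must include a rule for blanks. It does not remove the point: the design uses the stratum, the model omits it, and including it is almost costless when no student is lost.

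Two stronger readings should be resisted. A reader might infer that analysing without the stratification factor biases the estimate or makes the p-values too small. It does neither: random assignment protects the estimate, and any distortion of the standard error under balanced strata is conservative. A reader might also infer a material loss of power or intervals many percent too wide. The documents give no gap or correlation that would support this, and no figures are offered here for gaps above 0.5 SD.

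**Conclusion.** The omission is real and of low severity: worth considering, not a flaw that threatens the result. With balance within strata, the planned standard errors are somewhat too large on outcomes that the stratum predicts beyond pre-test. Without forced balance they are valid, and the gain from adding the stratum is smaller or nil.

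For gaps up to 0.5 SD that are similar at both tests, the excess width is about 1% or less only if the pre-post correlation is about 0.5 or more. It approaches 3% if the correlation is near zero, or if a gap of 0.5 residual SD survives pre-test adjustment. A low correlation cannot be excluded, since the two intention outcomes in section 10 are single items. These sizes rest wholly on assumed values. The omission itself and its direction do not.

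**What to change.** Change the covariate sentence in 11.1 to: *For each outcome, the model will include study arm, the corresponding pre-test measure, and the sexual activity stratum as used at randomisation (ever / never).*

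Then:
- Carry the value used for allocation into the analysis file.
- State which of the two items in 10.1 defined the stratum.
- Add a rule for blanks: *Students who skipped the sexual activity item are analysed in the stratum in which they were allocated, or as a separate category if allocated outside both strata; no randomised student is dropped for a blank stratum value.*

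The cost is a few sentences and no new data. It uses one degree of freedom, or two with a separate category. If the stratum adds nothing, one degree of freedom costs between 0% (balanced strata) and about 0.2% (balance not forced) in interval width at an assumed N=300. A second would cost about the same again.

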9 PARTICIPANT REIMBURSEMENT

Participants will be compensated with a \$10 gift card for the pre-test assessment and a \$10 gift card for the intervention and immediate post-test assessment.

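### Does assigning arms before the single session that holds both the programme and the only post-test put the HEART comparison at risk from lost outcomes?

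*Combined protocol and SAP*

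**What the plan says.** Section 8 gives the order of events. After the pre-test, "Participants will then be randomly assigned to either the HEART for Teens online program or to an attention-matched control program", with strata formed from the sexual-activity answer in the pre-test survey. The day of assignment is not given. The next step is "Approximately one week after pre-test, participants will complete the online intervention on a study-provided netbook computer as well as a computerized Qualtrics post-test survey", in small classroom groups.

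Section 4.1 limits the outcome times: "Participants will be assessed at pre-test and immediate-post test". Section 9 pays one "gift card for the intervention and immediate post-test assessment", so programme and post-test are treated as one visit. Section 15.1 tells students that "they can skip any items that make them uncomfortable or stop their participation at any time".

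Section 11.1 regresses each post-test outcome on arm and its pre-test value. It names no analysis set and no missing-data method. Section 14 has the team review data completeness weekly or as needed, without a step for recovering a missed post-test. Section 11.2 lets consent set the sample size, and section 4.2 gives the number approached ("n recruited = 754").

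**The concern.** Up to about a week can pass between assignment and the only occasion on which an outcome is measured. Two kinds of student could be randomised and have no outcome: those absent on the day, and those who stop and do not take the post-test. A regression on post-test scores drops both by default.

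The second kind is the more worrying. The arms differ in just the feature that might make a teenager stop, namely sexual-health content against academic-mindset content. If students who dislike the HEART material leave and would have scored lower, those who remain in HEART look better than everyone assigned to it. Adjusting for the pre-test does not remove this, because the reaction comes after the pre-test. At stake would be a biased estimate of preliminary efficacy (Aim 2), probably in HEART's favour, with no later assessment to repair it.

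**Working it through.** The plan states no sample size calculation, power, effect size or attrition rate, so there is no figure of its own to reproduce. Apart from the 754, every input below is an assumption.

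**Absence before the session**

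If half of the 754 take part, 377 are assigned. Absence of 5% to 15% removes 377 × 0.05 ≈ 19 to 377 × 0.15 ≈ 57 students. The cost is precision. At 10% absence the standard error grows by a factor of 1/√0.9 ≈ 1.05, and power for an assumed unadjusted effect of d = 0.3 goes from 83% to 79%.

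Suppose assignment moved to the start of the session. The same students would be absent, and the same number would be analysed. If the session used a prepared list linking participant IDs to arms, that would be close to the SPSS allocation already planned. The absentees would only cease to be counted as randomised. Comparability suffers only if absence depends on arm, which requires students to know their arm in advance, and no section says they do.

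**Stopping during the session**

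Set the mean of students who stay at 0 and of those who leave at −s (in SD, given pre-test). Let q be the share who leave without a post-test. In one arm, the complete-case mean minus the mean of all assigned is q × s. The bias in the difference between arms is

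q_HEART × s_HEART − q_control × s_control,

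which is 0 when loss and gap are the same in both arms. Taking all the loss as extra loss in HEART:

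| Extra loss in HEART | s = 0.5 SD | s = 0.8 SD |
|---|---|---|
| 1% | 0.005 | 0.008 |
| 5% | 0.025 | 0.040 |
| 10% | 0.050 | 0.080 |

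**Against sampling error**

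With 188 per arm and an assumed pre-post correlation of 0.6, SE = √(2/188 × (1 − 0.6²)) = 0.0825 SD. The two-sided false-positive rate under a bias b is P(Z > 1.96 − b/SE) + P(Z < −1.96 − b/SE):

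- b = 0.008: b/SE = 0.10, rate 5.1%
- b = 0.025: b/SE = 0.30, rate 6.1%
- b = 0.080: b/SE = 0.97, rate 16.3%

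Over 25% to 75% participation and correlations of 0.5 to 0.7, the last rate runs from 9.7% to 26.5%.

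The worst case is demanding. With a correlation of 0.6 the residual SD is √(1 − 0.36) = 0.8, so a gap of 0.8 SD is one full residual SD. It also needs 10 points more loss in HEART than in control within a single sitting.

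**What post-testing early leavers would gain**

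If a fraction r of leavers still took the post-test, the bias would be q × s − s × q × r / (1 − q(1 − r)). With r = 0.7:

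- q = 0.10, s = 0.8: 0.080 − 0.056/0.97 = 0.022
- q = 0.05, s = 0.5: 0.025 − 0.0175/0.985 = 0.007

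This assumes that leavers who accept the post-test resemble those who refuse it. That is doubtful if they left because of the content, so these are favourable figures.

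**The case for a change.** The strongest case for acting is that the gap is real on the text and cheap to close. No section offers the post-test to a student who stops the programme, defines who is analysed, or says how missing scores are handled. The arms do differ in content, section 15.1 itself names discomfort with sensitive questions as a risk, and early stopping by arm also bears on the feasibility and acceptability aim. A few sentences would settle it.

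The silence is real, and the possibility of loss that differs by arm stands. Three things limit its weight.

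- The right to stop appears where section 15.1 discusses discomfort with survey questions, and the surveys are not described as differing by arm. Stopping participation most naturally means leaving the study, and such a student could not simply be post-tested. A student who leaves the programme but would take the post-test is a narrower case that the documents never describe.
- Section 8 gives an approximate interval and small-group sittings. That neither provides for an absent student to join another group nor rules it out.
- The missing wording is an unstated detail. It is not a stated rule that produces a wrong answer. Analysing those with a post-test by assigned arm, and reporting by arm how many were assigned, stopped and lacked a post-test, is what an analyst would ordinarily do.

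**Conclusion.** No change to the plan is needed. Assignment before the session is not in itself a flaw, and moving it would recover no outcomes. What the plan leaves open is whether early leavers are offered the post-test and which students form the analysis set. Both are gaps in detail that competent conduct and reporting would fill.

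The likely bias is negligible: 0.005 to 0.008 SD at 1 point more loss in HEART, about a tenth of a standard error. It becomes material only under assumptions that the documents do not support, such as 10 points more loss in HEART in one sitting with a 0.8 SD gap (0.08 SD, false-positive rate about 16%). The conclusion rests on students not knowing their arm before the session, on which the documents are silent, and on little difference between arms in loss during one supervised school session. If the reported flow by arm showed a marked imbalance in missing post-tests, the efficacy estimates would need to be read with that in mind.

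### Programme and post-test are taken in small groups whose arm make-up is not stated, and the planned regression has no session term; if sessions are largely single-arm, the standard errors could be too small.

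*Combined protocol and SAP*

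**What the plan says.** All the design facts come from the combined protocol and SAP.

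- **Unit of randomisation (section 8).** Students are allocated one by one, after the pre-test: "Participants will then be randomly assigned to either the HEART for Teens online program or to an attention-matched control program". The mechanism is software allocation: "Random assignment to study condition will be conducted using random sampling and allocation procedures in SPSS version 24". The only stratification factor is sexual activity status. School, class and session are not used.
- **Delivery and measurement (section 8).** About a week after the pre-test, each student works through the assigned programme on a netbook "as well as a computerized Qualtrics post-test survey in a small group classroom setting". Within the room, delivery is individual: "Participants will use headphones to listen to program content and to control for any outside noise".
- **Sessions.** Section 8 does not give the size or number of groups, how students are assigned to them, or whether a group contains one arm or both. No session identifier is mentioned.
- **Analysis (section 11.1).** For efficacy, "linear regression analyses will be utilized to compute adjusted means and mean differences between intervention and control groups". On covariates: "For each outcome, the corresponding pre-test measure will be included as a covariate". No session term, mixed model or cluster-robust standard error is mentioned.
- **Size (sections 4.2 and 11.2).** The only number is "n recruited = 754". The final sample depends on consent, and no target, power, alpha or ICC is stated.

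**The concern.** Students who sit the programme and post-test together share staff, time of day, peers and any disruption. The outcomes in section 10 are mostly self-reports (intentions, self-efficacy, attitudes, norms, assertiveness), with a short knowledge test. They are answered in that same sitting, so a shared influence could move a whole group's answers. Ordinary regression assumes independent residuals.

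Whether this matters for the comparison of arms depends on how sessions are filled. Allocation precedes the session by about a week, so staff could schedule the two programmes in separate sessions, and nothing in section 8 rules this out. Session would then be nested in arm, session effects would not cancel between arms, and the ordinary standard error would omit them.

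At stake are the p-values and confidence intervals for Aim 2. If no session ID is kept, the problem could be hard to diagnose or repair afterwards.

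**Working it through.** The plan gives no sample-size or precision figure to reproduce, so the check asks how the planned regression behaves under each possible session make-up.

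**Inputs**
- From the documents: individual randomisation, small-group sessions, regression on arm plus pre-test value, and 754 as the ceiling on N.
- Assumed, because the documents do not give them: two-sided alpha 0.05, 1:1 allocation, session size m, residual session ICC after pre-test adjustment, analysed N, and pre/post correlation (0.6 in the simulations).

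**Case 1: single-arm sessions**

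The variance of the arm difference is multiplied by DE = 1 + (m − 1) × ICC. The correct standard error is √DE times the planned one. The true type I error of a nominal 5% test is 2 × [1 − Φ(1.96/√DE)].

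| m | ICC | DE | √DE | 1.96/√DE | True type I error |
|---|---|---|---|---|---|
| 8 | 0.02 | 1 + 7 × 0.02 = 1.14 | 1.07 | 1.84 | 6.6% |
| 8 | 0.05 | 1 + 7 × 0.05 = 1.35 | 1.16 | 1.69 | 9.2% |
| 15 | 0.02 | 1 + 14 × 0.02 = 1.28 | 1.13 | 1.73 | 8.3% |
| 15 | 0.05 | 1 + 14 × 0.05 = 1.70 | 1.30 | 1.50 | 13.3% |

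At the low end of the wider set of assumptions (m = 5, ICC 0.01), DE is 1.04 and the type I error is 5.5%, so the effect can also be negligible.

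**Case 2: both arms in each session**

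With exact balance within sessions, session effects cancel from the contrast. The true variance is about (1 − ICC) times what ordinary regression reports. At ICC 0.05 the statistic to compare is 1.96/√0.95 = 2.01, giving a type I error of about 4.4%, which is slightly conservative.

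**Simulation of the planned model**

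Outcome on arm and pre-test with ordinary standard errors; 40 sessions and 4,000 runs per setting. The Monte Carlo standard error near 5% is √(0.05 × 0.95/4000) = 0.3 percentage points. With m = 20 the simulated total is 40 × 20 = 800, a little above the 754 ceiling.

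| m | ICC | Single-arm sessions | Mixed by chance | Balanced by arm |
|---|---|---|---|---|
| 10 | 0.02 | 7.7% | 5.1% | 4.5% |
| 10 | 0.05 | 10.4% | 5.1% | 4.9% |
| 20 | 0.02 | 9.7% | 5.0% | 4.5% |
| 20 | 0.05 | 16.7% | 4.8% | 4.1% |

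Pre-existing similarity among classmates (ICC 0.10), with individual randomisation and no effect of the session itself, gave 4.6% (m = 10) and 4.3% (m = 20).

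**Power once clustering is respected (illustration)**

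Take N = 400 and d = 0.3, using Φ(d√(n/2) − 1.96) with n per arm.
- Independent data, n = 200: Φ(0.3 × 10 − 1.96) = Φ(1.04) = 85.1%.
- Single-arm sessions, m = 10, ICC 0.05: DE = 1.45 and effective n = 200/1.45 = 138, so power is Φ(0.3 × √69 − 1.96) = Φ(0.53) = 70.2%.

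**The case against.** The strongest reply is that this is an individually randomised trial with individually delivered content. Each student has a netbook and headphones, and nowhere do the documents say that sessions are run by arm. Inflation needs two things that they do not establish: sessions that are largely single-arm, and a real effect of the session on the answers. Mixing by chance is enough to keep the planned regression valid. Similarity that existed before randomisation, within class or school, does no harm by itself. Headphone delivery may keep the session ICC small. The study also describes itself as preliminary (sections 3 and 11.2).

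Most of this stands, and it limits the point to a conditional one. A reader might infer more than the documents support:

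- *That the error bars are wrong.* They are wrong only under a session make-up that the plan neither adopts nor excludes.
- *That false positives are inflated on every outcome.* That would require a positive session-induced ICC for each one, and none is known.
- *That mixed sessions are also a fault because session variance stays in the residual.* The test is then at or slightly below its nominal level.
- *That much larger inflation should be expected.* Such figures need larger groups or ICCs, and large groups sit poorly with a plan that calls its groups small.

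The reply does not settle the matter. Headphones make mixed sessions possible but do not ensure them, and they do not remove shared staff, peers or disruption. A preliminary aim does not make an interval that is too narrow acceptable.

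**Conclusion.** The point holds as a conditional risk. The plan does not state the one fact on which the validity of its standard errors depends, namely the arm make-up of the sessions, and its model does not guard against the unfavourable case.

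With mixed sessions there is no validity problem. With largely single-arm sessions and some session-induced correlation, the type I error is about 6.6% to 13.3% over the assumed range (m 8 to 15, residual ICC 0.02 to 0.05). The actual size cannot be found from the documents, because group size, ICC, alpha, analysed N and pre/post correlation are all assumed. This justifies a cheap improvement to the plan. It does not justify a statement that the trial's inference is invalid.

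**What to change.** 1. In section 8, state how sessions are formed, and record a session ID for every student at post-test in Qualtrics.
2. In section 11.1, fit each outcome with a session random intercept beside the pre-test value and arm, using small-sample degrees of freedom. The MIXED procedure in SPSS, the package already planned, can fit this model, which is valid under either session make-up.
3. Do not use a session fixed effect if sessions are single-arm, because it is then confounded with arm.
4. Report the number and size of sessions and how many held one arm or both.

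Mixing the arms within sessions would largely remove the problem by design. However, students side by side on different programmes may see or discuss the other arm's material. The investigators should weigh that risk of contamination; mixing is an option, not a requirement.

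The cost is one ID field and one model term, with no extra participants or visits. If sessions are mixed, the change costs almost nothing. If they are single-arm, standard errors become about 7% to 30% larger over the assumed range (√1.14 = 1.07 to √1.70 = 1.30). That corrects the error bars but lowers power.
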